10. Observer measurements will be recorded simultaneously by the observers on separate sheets. They will be checked immediately by the nurse supervisor and, if they differ by more than 4 mmHg, they will be taken again. Observers will be blinded from each other's measurements and from the device measurements.
11. Starting with the observers, the nurse supervisor will record the measurements sequentially by the supervisor, alternating between observers and the supervisors' reading of the device in the order BPA, BPB, BP1, BP2, BP3, BP4, BP5, BP6 and BP7 on Form 2.
12. **The nurse supervisor** will take a picture of the device measurements and those photographs will be emailed to the research assistant.
13. On a separate sheet, **the nurse supervisor** will keep a running total of the number of subjects recruited in the Low (LL and L), Medium (M), and High (H and HH), ranges for SBP (Box 219) and DBP (Box 220) on Form 2.
14. If any of the following occur during the study, **the nurse supervisor** will circle the appropriate item in Box 287 on Form 2 and exclude the subject:
 - Circle *Arrhythmias* if the subject is not in sinus rhythm throughout the study.
 - Circle *Device failure* if the device fails to record a measurement after three successive attempts.
 - Circle *Poor quality sounds* if the Korotkoff sounds are difficult to auscultate, regardless of the reason.
 - Circle *Observers disagreement* if the observers differ by more than 4 mmHg twice in the same subject.
 - Circle *Other* if the subject does not complete the study for any reason other than those listed and record the reason in Box 288.
15. In the event that an abnormal blood pressure reading is detected (e.g. if the blood pressure is outside clinically normal range for a specific client), one of the observers will

re-take the blood pressure to determine if the abnormal reading is accurate. If the abnormal blood pressure measurement is accurate, the **nurse supervisor** will take appropriate action as directed by professional standards. The abnormal blood pressure data will be recorded on Form 2.

Data Checking

During the data collection process, researchers will check the data daily to ensure the following as per the ESH-IP (O'Brien et al., 2010):

1. Ensure that the difference between the range with the highest count and lowest count does not exceed 19.

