Observer difference	247	248	249	250	251	252	253	254
	BP2		BP4		BP6		Difference	
	SBP	DBP	SBP	DBP	SBP	DBP	A	0–5 mmHg
Device	255	256	257	258	259	260	B	6–10 mmHg
Device–Previous observer	261	262	263	264	265	266	C	11–15 mmHg
Device–Next observer	267	268	269	270	271	272	D	> 15 mmHg
Error group	A B C D 273	A B C D 274	A B C D 275	A B C D 276	A B C D 277	A B C D 278	Within 5 mmHg	
Observer value	281	282	283	284	285	286	SBP	DBP

Boxes 239–246: Enter the rounded up averages of Boxes 223 and 231, of Boxes 224 and 232, of Boxes 225 and 233, of Boxes 226 and 234, of Boxes 227 and 235, of Boxes 228 and 236, of Boxes 229 and 237 and of Boxes 230 and 238 respectively.

Boxes 247–254: Enter the differences Box 223–Box 231, Box 224–Box 232, Box 225–Box 233, Box 226–Box 234, Box 227–Box 235, Box 228–Box 236, Box 229–Box 237, and Box 230–Box 238 respectively.

Boxes 261–266: Enter the 'Device–Previous Observer Mean' differences. These are Box 255–Box 239, Box 256–Box 240, Box 257–Box 241, Box 258–Box 242, Box 259–Box 243, and Box 260–Box 244 respectively.

Boxes 267–272: Enter the 'Device–Next Observer Mean' differences. These are Box 255–Box 241, Box 256–Box 242, Box 257–Box 243, Box 258–Box 244, Box 259–Box 245, and Box 260–Box 246 respectively.

Each device measurement is compared to the nearer of the previous and next observer measurement. As described below, the smaller error is circled and the corresponding observer measurement is copied to aid the analysis.

Box 273: First, circle the smaller value, in absolute terms, of Boxes 261 and 267 (Box 261 if both are the same). Then circle A if this is less than or equal to 5, B if this is 6–10, C if this is 11–15 or D if this is greater than 15.

Boxes 274–278: Circle A, B, C or D, as described for Box 273, based on the smallest absolute values (also circled) of Boxes 261 and 268, Boxes 263 and 269, Boxes 264 and 270, Boxes 265 and 271 and Boxes 266 and 272 respectively.

Box 279: Enter the number of 'A's circled in Boxes 273, 275 and 277.

Box 280: Enter the number of 'A's circled in Boxes 274, 276 and 278.

The numbers of 'A's, 'B's and 'C's will be used in the analysis to calculate the number of device-observer differences within 5 mmHg, 10 mmHg and 15 mmHg.

Box 281: Enter the value in Box 239 if Box 261 is circled or Box 241 if Box 267 is circled.

Box 282: Enter the value in Box 240 if Box 262 is circled or Box 242 if Box 268 is circled.

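### Form 2 as written grades the first diastolic reading (Box 274) partly on a systolic difference: Box 261 is named where Box 262 is needed

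*Combined protocol and SAP*

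**What the plan says.** In the validation section of Form 2 (Appendix M), Boxes 255–260 hold the device readings, alternating systolic and diastolic. Boxes 261–266 are the differences from the previous observer mean: "These are Box 255–Box 239, Box 256–Box 240", and so on. Boxes 267–272 are the differences from the next observer mean: "These are Box 255–Box 241, Box 256–Box 242", and so on. The principle is then stated: "Each device measurement is compared to the nearer of the previous and next observer measurement".

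Boxes 273–278 turn the smaller absolute difference into a letter from A to D. Box 273, the first systolic grade, uses Boxes 261 and 267. Box 274, the first diastolic grade, is "based on the smallest absolute values (also circled) of Boxes 261 and 268". The observer value that goes with Box 274 is Box 282: "Enter the value in Box 240 if Box 262 is circled or Box 242 if Box 268 is circled". Box 280, the diastolic score for the subject, is defined as "Enter the number of 'A's circled in Boxes 274, 276 and 278".

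Form 3 (Appendix N) builds the diastolic Part 1 counts (Boxes 366–368) from the letters in Boxes 274, 276 and 278, and the diastolic Part 2 counts (Boxes 376–377) from Box 280. These lead to Box 379 and the overall result in Box 380. The diastolic mean and SD (Boxes 370–371) use whichever of Boxes 262 and 268 is circled.

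**The concern.** Box 274 is a diastolic grade, yet one of the two differences named for it is systolic. A subject whose first diastolic reading is badly wrong can receive an A because the systolic reading was close. A good diastolic reading can lose its A because the correct comparison, Box 262, is never consulted.

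The letters, not the raw differences, supply the counts that decide a pass. The Study purpose section says that the sponsor will seek approval from Health Canada and the FDA if the algorithm is shown to be accurate. An instruction that the supervisor follows for every subject should therefore not depend on the reader inferring what was meant.

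**Working it through.** **Box trace.** From the definitions in Form 2:

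- Box 261 = Box 255 − Box 239: systolic, BP2 minus BP1.
- Box 262 = Box 256 − Box 240: diastolic, BP2 minus BP1.
- Box 268 = Box 256 − Box 242: diastolic, BP2 minus BP3.

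| Grade | Pressure and reading | Pair named for grading | Pair named for the matching observer value |
|---|---|---|---|
| 273 | SBP, BP2 | 261, 267 | 261, 267 (Box 281) |
| 274 | DBP, BP2 | **261**, 268 | **262**, 268 (Box 282) |
| 275 | SBP, BP4 | 263, 269 | 263, 269 (Box 283) |
| 276 | DBP, BP4 | 264, 270 | 264, 270 (Box 284) |
| 277 | SBP, BP6 | 265, 271 | 265, 271 (Box 285) |
| 278 | DBP, BP6 | 266, 272 | 266, 272 (Box 286) |

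Five of six pairs agree. As written, Box 261 is used twice and Box 262 never. With 262 in place of 261, each of Boxes 261–272 is used exactly once.

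**Exposure.** Appendix O sets 85 subjects and at least 255 pairs (85 × 3). Box 274 supplies 85 of 255 diastolic Part 1 grades and one of the three grades in each subject's Part 2 score.

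**Direction.** Both are possible:

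- 262 = +12, 268 = +11, 261 = −1. Correct: min(12, 11) = 11, grade C. As written: min(1, 11) = 1, grade A.
- 262 = +2, 268 = +8, 261 = +12. Correct: min(2, 8) = 2, grade A. As written: min(12, 8) = 8, grade B.

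**Knock-on gaps.** If Box 261 is circled for Box 274, neither 262 nor 268 is circled, so Box 282 and the diastolic mean and SD have no source for that reading. If Box 267 was circled for Box 273, Boxes 261 and 267 are then both circled and Box 281 has two candidates.

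**Size under assumed errors.** The documents give no device or observer error SDs, so everything from here is illustration. Device error was simulated as bias plus between-subject and within-subject terms, with four observer readings per subject, values rounded to 1 mmHg, and systolic–diastolic correlation of 0, 0.5 or 0.7. Over 78 scenarios:

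| | No bias | Bias up to 15 SBP or 8 DBP |
|---|---|---|
| Box 274 grades that change | 10–36% | 10–49% |
| Net change in A grades per 85 | −2.5 to +17 | −10 to +26 |
| Subjects with Box 261 circled for Box 274 | 31–69% | 10–74% |

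In the four settings checked for it, Box 281 was ambiguous in 7–20% of subjects.

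Pass probabilities use the Appendix O limits only: at least two of 188/224/247, all of 167/209/240, at least 62 subjects with two or three readings within 5 mmHg, and at most 8 with none. Overall pass requires both pressures to pass. The figures assume that blank Box 282 entries are filled in without regrading Box 274, in all 85 subjects. SDs are between-subject/within-subject/observer in mmHg; correlation is 0.7.

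| Systolic SDs | Diastolic SDs | Overall pass, correct | Overall pass, as written |
|---|---|---|---|
| 3/3/3 | 3/3/3 | 1.00 | 1.00 |
| 4/4/3 | 4/4/3 | 0.97 | 0.98 |
| 4.5/4.5/3 | 4.5/4.5/3 | 0.70 | 0.79 |
| 5/5/3 | 5/5/3 | 0.20 | 0.31 |
| 5.5/5.5/3 | 5.5/5.5/3 | 0.01 | 0.03 |
| 6/6/3 | 6/6/3 | 0 | 0 |
| 4/4/3 | 5/5/3 | 0.38 | 0.78 |
| 5/5/3 | 4/4/3 | 0.38 | 0.38 |

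With equal SDs, the shift at SD 4.25 is 0.930 − 0.891 = 0.039 at correlation 0.7 and 0.936 − 0.880 = 0.056 with independent errors. At 5.5 it is 0.032 − 0.012 = 0.020 and 0.025 − 0.004 = 0.021. Among the SDs tried, the shift exceeds 0.05 only from 4.5 to 5.25 at correlation 0.7, and from 4.25 to 5.25 with independent errors.

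The rule can also count against the device. With systolic 10/7/5 and diastolic 5/4/3, diastolic pass falls from 0.70 to 0.65 at correlation 0.7. At correlation 0 the same SDs give a rise, from 0.69 to 0.77. At correlation 0.7 overall pass is 0 under either rule, because systolic fails.

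**Detection.** In the cases quoted at correlation 0.7, Box 261 is circled for Box 274 in at least 31% of subjects. The chance of no blank Box 282 in the first 10 subjects is therefore at most (1 − 0.31)^10 = 0.024. At the lowest rate in any scenario, 10%, the chance of none in 85 is 0.9^85 = 0.0001.

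**The case against.** The strongest reply is that the form leaves no real doubt about the intended rule. The general principle comes just before the disputed line, the other five pairs follow it, Boxes 282 and 370–371 name Box 262, and Box 366 is worded as a count of diastolic differences. The digit may even be a transcription fault in the text rather than an error in the form itself.

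The literal rule also tends to expose itself. The Data Checking section says that "researchers will check the data daily to ensure the following as per the ESH-IP", including "Ensure that the difference between the range with the highest count and lowest count does not exceed 19" and the overall diastolic range. The matching Form 3 entries, Boxes 350–354, draw on Box 282, so blanks would probably be noticed. Readings are recorded, so any error can be undone. On this view it is a minor erratum, and the larger pass-rate shifts need an unlikely chain of events.

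Most of this stands: misprint is the likeliest explanation and an undetected effect is unlikely. What remains is that these checks look at observer pressures, not letters. Someone could fill a blank Box 282 by hand and leave the wrong letter in Box 274, and nothing in the plan calls for Box 274 to be regraded. A spreadsheet or program written from the form could carry the same fault.

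**Conclusion.** The concern holds: the rule for Box 274 is wrong as written and contradicts the rest of Forms 2 and 3. That conclusion rests on the box definitions alone, subject to checking the digit against the original form.

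The practical effect is conditional. It arises only if the form is completed or programmed literally and Box 274 is not regraded. Even then it has no fixed direction, and it matters to the verdict only when diastolic error is close to the Appendix O limits. The largest shift among the tabulated cases, 0.38 to 0.78, needs diastolic error near the limits and systolic error clearly inside them. It should be corrected because it sits in a decisive rule and costs almost nothing to put right, not because harm is likely.

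**What to change.** 1. Check the digit against the original form.
2. In Form 2, Boxes 274–278, change the first pair from Boxes 261 and 268 to Boxes 262 and 268. Make the same change in any spreadsheet or program built from the form.
3. Before completing Form 3, recalculate Boxes 274, 280 and 282 for every subject from Boxes 256, 240 and 242 (Box 280 also takes the letters in Boxes 276 and 278). Confirm that Box 281 follows the value circled for Box 273.
4. Add a line to the daily data check: Box 282 is filled, and the letter in Box 274 agrees with Boxes 262 and 268.

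The cost is one digit, one line in the daily check, and a recalculation from values already recorded. No new data are needed.

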http://www.contecmed.com/index.php?page=shop.product_details&flypage=flypage.tpl&product_id=118&category_id=27&option=com_virtuemart&Itemid=618

Heartbeat's intent is that the current blood pressure reading would then be made available to both the client and the health provider through separate web-based interfaces. Providers would be able to log onto the HeartBeat web-based application from anywhere to review and monitor the blood pressure of multiple clients, while clients can log onto the application to track their own measurements.

2. Study purpose

Though the Contec finger pulse oximeter has been approved for use by Health Canada (Licence No. 90629) and the FDA (<https://www.accessdata.fda.gov/scripts/cdrh/cfdocs/cfRL/rl.cfm?lid=465210&lpcd=DQA>), the proprietary algorithm developed by Heartbeat Technologies Ltd. has not been approved for use. The purpose of this study is to validate the accuracy of the algorithm as compared with the standard manual sphygmomanometer with stethoscope for measuring blood pressure. If the algorithm is shown to be accurate, Heartbeat Technologies Ltd. will apply to Health Canada and the FDA for approval for its use to measure blood pressure.

3. Study Design/Methodology

Trial registration

This study will be registered with ClinicalTrials.gov as it is one of two registered bodies approved and recommended by Health Canada. This will serve as a publicly accessible platform for patients and practitioners to understand the current study's objectives and goals, and be kept informed of the results.

Protocol

The European Society of Hypertension International Protocol revision 2010 for the validation of blood pressure measuring devices in adults (ESH-IP) (**Appendix A**) (O'Brien et al., 2010) will be followed precisely, except it will be modified to follow the extra guidance in the international consensus statement for validation (**Appendix B**) (Stergiou et al., 2018). The international consensus statement (Stergiou et al., 2018) reviewed the adequacy of the number of participants in a variety of established protocols including the ESH-IP, and recommended that, to increase study power and accuracy, the number of participants in a study following the ESH-IP should be at least 85 rather than 33 as in the 2010 version of the ESH-IP.

Setting and clinicians

Study site

The study site will be a room with a comfortable temperature and with no noise or other influences that may cause disturbance, such as telephones.

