The pulse oximeter, the Heartbeat application (MediBeat), and the supervisor's smartphone (Samsung Galaxy Xcover 4 with Bluetooth connectivity) will be charged, and tested each day of interactions with participants. Prior to conducting the study session, the equipment will have to be calibrated for each participant. The first step of the calibration process is to manually enter the reference data (date of birth, height, weight, baseline manual blood pressure reading and heart rate). Once data is entered, and participant has been given 10 minutes of rest, the nurse supervisor will ensure the participant is seated comfortably, with their legs uncrossed, back supported, and their arm rested on the table at heart level. The nurse supervisor will then attach the Contec finger pulse oximeter to the participant's finger (opposite to the arm with the manual blood pressure cuff) and wait for a few seconds, to make sure a stable signal is received, and the device displays both the participant's pulse and SpO₂ values. Once the values are displayed, the nurse supervisor will hit the "Add session" button, and choose the correct device to connect to via Bluetooth. The calibration process will begin, indicated by the orange background, and the MediBeat application will display the participant's heartrate and SpO₂ values. It is critical that the participant does not move during the calibration process, which will last just over 1 minute. The background of the application will turn blue once calibration has completed successfully.

Recruitment plan

Inclusion/Exclusion Criteria

Healthy participants who are over the age of 25 and live or work in the North Simcoe Muskoka and Markham regions will be recruited to participate in this study. As outlined in the ESH-IP, only healthy subjects will be included this study; those who have heart arrhythmias, atrial fibrillations or atrial flutters, an inaudible Korotkoff sound, wounds of the upper arms/wrists, missing fingers, and/or an arm circumference of more than 55 cm will be excluded, in advance if at all possible, and at the study site if not previously excluded.

Recruitment will continue until the following quotas are met:

1. Numbers: At least 85 who fully complete the study protocol, and fall within the parameters listed in #3
2. Sex: At least 26 male and 26 female (each 30% of the total number of participants)

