3. Blood pressure range: 26 to 31 subjects in each of the three SBP and three DBP recruitment ranges as shown in Form 3 – Study Results (**Appendix N**):
 - Low blood pressure (systolic: 0-129, diastolic: 0-79)
 - Medium blood pressure (systolic: 130-160, diastolic: 80-100)
 - High blood pressure (systolic: 161 or higher, diastolic: 101 or higher).

Participant Remuneration

To thank participants for their valuable time, they will be provided with a \$50 VISA pre-paid gift card at the end of the study visit.

Recruitment Methods

Recruitment flyers (**Appendix E**) will also be posted in public spaces at corporate offices and medical clinics, who have agreed to participate within Central Ontario, including Markham, Toronto, and North Simcoe Muskoka.

Recruitment emails (**Appendix F**) will be sent to all relevant employees located at corporate offices and medical clinics, who have agreed to participate within Central Ontario, including Markham, Toronto, and North Simcoe Muskoka, with a link to [contact] to indicate interest. Recruitment will be a two-step process.

Clinical staff, from clinics who have agreed to participate, will be provided with a short script (**Appendix G**) and Frequently Asked Questions (FAQ) document (**Appendix H**) to assist with the recruitment process. Individuals interested in participating can submit a consent to contact form (**Appendix I**) to the clinic staff, who will scan and send the forms to the research team. **Research assistant** will call individuals who had expressed their interest in participating to further explain the study (**Appendix J**) and ask if they would like to participate. The research assistant will then inform them about the consent form (**Appendix K**) that they will be asked to sign at the study site. The research assistant will provide the participant with information about a scheduled time for participating in the study and directions.

Interactions with participants and Data collection

Form 1 - Device information

Prior to the first interaction with a participant, the supervisor will fill in the information about the device in Form 1 of the ESH-IP (**Appendix D**). As noted above, the Contec CMS50EW device is an electronic finger pulse oximeter (Contec Medical Systems Co., Ltd, Qianhuangdao, China) that generates a PPG, which is then sent to HeartBeat's proprietary algorithm to calculate blood pressure.

Confirmation of appropriate setting conditions

[figure not shown]

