Box 308: The number of subjects excluded with *Cuff size availability* circled in *Box 287*.

Box 309: The number of subjects excluded with *Observer disagreement* circled in *Box 287*.

Box 310: The number of subjects excluded with *Distribution* circled in *Box 287*.

Box 311: The number of subjects excluded with *Other reasons* circled in *Box 287*. A summary of those reasons must be provided in Box 313.

Box 312: The total recruited equals the number screened (Box 301) less the number excluded (Box 302). This should equal 33 except in validations in some specific populations.

Box 313: A summary of why those counted in Box 311 were excluded (*Box 288*).

Boxes 314–323: In a completed study in a general adult population, the sum of Boxes 314 and 315, Box 316, the sum of Boxes 317 and 318, the sum of Boxes 319 and 320, Box 321 and the sum of Boxes 322 and 323 must each be between 10 and 12. The sum of Boxes 314, 318, 319 and 323 must be at most 4. The sum of Boxes 314–318 and the sum of Boxes 319–323 must each be exactly 33. Studies in specific populations may have different restrictions and totals (*Boxes 219 and 220 – Form 2 for each included subject*).

Boxes 324–329: The number of subjects in each range on antihypertensive medication (*Boxes 207, 219 and 220*).

Table 2 Subject details

Sex	Male : Female	330	
Age (years)	Range (Low : High)	331	
	Mean (SD)	332	
Arm circumference (cm)	Range (Low : High)	333	
	Mean (SD)	334	
Cuff for test device (Upper arm devices only)	Small	335	— — cm
	Standard	336	— — cm
	Large	337	— — cm
	Other	338	— — cm
Wrist circumference (cm) (Wrist devices only)	Range (Low : High)	339	
	Mean (SD)	340	
Recruitment BP (mmHg)	Range (Low : High)	341	SBP
		342	DBP
	Mean (SD)	343	
		344	

Note: The values in Boxes 314–380 refer only to the final recruited subjects, each of whom contributes SBP and DBP measurements for analysis. Excluded subjects are not included in any of this analysis.

Box 330: Enter the number of males, a colon and the number of females. They should total 33 except in validations in some specific populations. If the minimum requirements (10 for a general population) are not met, subjects must be replaced as necessary (Box 206).

Box 331: Enter the age of the youngest subject, a colon and the age of the oldest subject e.g. 31:74. Subjects outside the required range (25 and over for a general population) are not permitted (Box 205).

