Boxes 357–358: Enter the mean and, in parentheses, the SD of the observer differences. Values should be rounded up to one decimal place e.g. 0.3 (1.2) (Boxes 247, 249, 251 and 253 and Boxes 248, 250, 252 and 254).

Boxes 359: Enter the number of measurements that were repeated in the included subjects because observers were more than 4 mmHg apart.

Table 5 Validation results

Part 1		$\leq 5\text{mmHg}$	$\leq 10\text{mmHg}$	$\leq 15\text{mmHg}$	Grade 1	Mean	SD
Pass requirement	Two of	73	87	96			
	All of	65	81	93			
Achieved	SBP	360	361	362	363	364	365
	DBP	366	367	368	369	370	371
Part 2		$2/3 \leq 5\text{mmHg}$	$0/3 \leq 5\text{mmHg}$	Grade 2	Grade 3		
Pass requirement		≥ 24	≤ 3				
Achieved	SBP	372	373	374	375		
	DBP	376	377	378	379		
Part 3		Result					
		380					

In order for the device to pass, all protocol requirements must be fulfilled. A fail in any part will result in an overall fail

Box 360: Enter the number of SBP differences (at most 99) between observer and device measurements falling within 5 mmHg.
(The total number of *Boxes* 273, 275 and 277 circled A in the 33 subjects)

Box 361: Enter the number of SBP differences (at most 99) between observer and device measurements falling within 10 mmHg.
(The total number of *Boxes* 273, 275 and 277 circled A or B in the 33 subjects)

Box 362: Enter the number of SBP differences (at most 99) between observer and device measurements falling within 15 mmHg.
(The total number of *Boxes* 273, 275 and 277 circled A, B or C in the 33 subjects)

Box 363: If Boxes 360, 361 and 362 fulfil the Pass requirements, then this is 'Pass'; otherwise, it is 'Fail'.

Boxes 364–365: Enter the mean and standard deviation respectively of the 99 SBP differences between observer and device measurements. (Use data from circled *Boxes* 261 or 267, 263 or 269 and 265 or 271)

Box 366: Enter the number of DBP differences (at most 99) between observer and device measurements falling within 5 mmHg.
(The total number of *Boxes* 274, 276 and 278 circled A in the 33 subjects)

Box 367: Enter the number of DBP differences (at most 99) between observer and device measurements falling within 10 mmHg.
(The total number of *Boxes* 274, 276 and 278 circled A or B in the 33 subjects)

Box 368: Enter the number of DBP differences (at most 99) between observer and device measurements falling within 15 mmHg.
(The total number of *Boxes* 274, 276 and 278 circled A, B or C in the 33 subjects)

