Appendix O – International Protocol Accuracy Criteria

ESH International Protocol 2010			
Sequential Measurements			
IP Grading Part 1 - Minimum Requirements (at least 255 pairs of individual measurements)			
N	≤ 5 mmHg	≤ 10 mmHg	≤ 15 mmHg
Two of	188	224	247
All of	167	209	240
IP Grading Part 2 (85 subject mean pressures)			
N	$2/3 \leq 5$ mmHg		$0/3 \leq 5$ mmHg
At least	62		
At most			8
Recruitment Ranges (n = 85)			
SBP		DBP	
mmHg	Subjects	mmHg	Subjects
90*...129	26 – 31	40*...79	26 – 31
130...160	26 – 31	80...100	26 – 31
161...180*	26 – 31	101...130*	26 – 31
*	Altogether, up to 4 recruitment pressures are permitted to be outside these limits.		
Test Measurement Distribution			
SBP		DBP	
mmHg	Measurements	mmHg	Measurements
≤ 100	≥ 3	≤ 50	≥ 3
< 130	57 – 113*	< 80	57 – 113*
130...160	57 – 113*	80...100	57 – 113*
> 160	57 – 113*	> 100	57 – 113*
≥ 170	≥ 3	≥ 120	≥ 3
*	The difference between the maximum and minimum of these 3 counts for SBP and, separately, for DBP, must be less than or equal to 19.

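### Form 3 Table 1 still requires exactly 33 subjects with 10–12 per pressure range; the protocol body and Appendix O require at least 85 with 26–31, and no sentence says Appendix O overrides the form

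*Combined protocol and SAP*

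**What the plan says.** The Protocol subsection of section 3 adopts the ESH-IP with a stated modification: "the number of participants in a study following the ESH-IP should be at least 85 rather than 33". The Recruitment plan carries this through. Quota 1 asks for "At least 85 who fully complete the study protocol", and quota 3 asks for "26 to 31 subjects in each of the three SBP and three DBP recruitment ranges as shown in Form 3 – Study Results". Appendix O repeats 26–31 per range under a recruitment block set for n = 85.

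Form 3, Table 1 keeps the 33-subject values. On the total recruited, Box 312 says: "This should equal 33 except in validations in some specific populations". For Boxes 314–323, in a completed study of general adults, each of the six range sums "must each be between 10 and 12", and "The sum of Boxes 314–318 and the sum of Boxes 319–323 must each be exactly 33". Different limits are allowed only for studies in specific populations.

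Two further statements decide how much this matters. The Data Analysis subsection has the data analysed as Form 3 specifies, then bases passing on parts 1 and 2 of the Appendix O table. Form 3, Table 5 adds: "In order for the device to pass, all protocol requirements must be fulfilled".

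**The concern.** The composition of the final sample is defined twice, with values that exclude each other. The results form is an operative document: it is what the researchers will complete, and Boxes 314–380 are restricted to the final recruited subjects. A team that recruits exactly as planned will reach Table 1 and find that its sample breaks mandatory conditions of the form. It must then decide, after the data are in, which set of rules to ignore. The results are meant to support applications to Health Canada and the FDA. A results form that contradicts its own protocol on sample size and range composition is an avoidable weakness there.

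**Working it through.** **Inputs**

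| Item | Form 3, Table 1 | Recruitment plan and Appendix O |
|---|---|---|
| Total subjects | exactly 33 | at least 85 (Appendix O: n = 85) |
| Subjects per SBP or DBP range | 10–12 | 26–31 |

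**Step 1: reproduce the plan's own figure.** Scale the 33-subject limits by 85/33 and round to the nearest integer.

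- Lower limit: 10 × 85/33 = 25.76, which rounds to 26.
- Upper limit: 12 × 85/33 = 30.91, which rounds to 31.

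The 26–31 quota is therefore the Form 3 limit, rescaled. The part 1 and part 2 pass marks in Appendix O reproduce in the same way, using 255/99 for measurements (3 × 85 = 255; 3 × 33 = 99). For example, 73 × 255/99 = 188.03 gives 188, and 24 × 85/33 = 61.82 gives 62. So do the measurement distribution limits: 22 × 255/99 = 56.67 gives 57, and 44 × 255/99 = 113.33 gives 113. Appendix O was rescaled and Form 3 was not.

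**Step 2: compare totals.**

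- Form 3: 3 × 10 = 30 to 3 × 12 = 36, and within that exactly 33.
- Protocol: 3 × 26 = 78 to 3 × 31 = 93, and within that at least 85.

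The largest total that the Form 3 range limits allow (36) is below the smallest that the protocol's range quota allows (78).

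**Step 3: count the conditions broken.** The per-range limits do not overlap either (12 < 26). A sample that meets the protocol's quotas breaks all six range limits and both totals, which makes eight mandatory conditions. It also misses the expected value in Box 312.

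**Step 4: enumerate (low, medium, high) counts.**

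| Per-range limits | Required total | Ordered solutions |
|---|---|---|
| 10–12 | 33 | 7 |
| 10–12 | 85 | 0 |
| 26–31 | 33 | 0 |
| 26–31 | 85 | 27 (e.g. 26 + 28 + 31) |

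The last row shows that the form can be satisfied once its limits are rescaled.

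**Step 5: does the exception apply?** The study enrols healthy adults over 25 and names no special population. Box 331 of Form 3 itself treats 25 and over as the general population. The form's provisions for larger samples (Boxes 314–323, the note under Table 3, and the closing line after Box 380) are all confined to specific populations.

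**Step 6: does anything set Table 1 aside?** The Data Analysis subsection names Appendix O for passing parts 1 and 2. No sentence says that Appendix O replaces the Table 1 limits. The List of Appendices marks Appendix M as amended but not Appendix N.

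**The case against.** The strongest reply is that the conflict is resolved in the body of the protocol. The Protocol subsection says the ESH-IP is modified and names the change from 33 to 85. Form 3 is that protocol's standard form, and the quotas and Appendix O agree with each other. This stands, and it limits the severity: a careful reader can recover the intended rule. It does not correct the form, whose mandatory limits remain in the specified analysis with no statement of precedence.

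Three stronger readings are tempting, and the documents do not support them.

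- *The device could never pass.* The Data Analysis subsection rests passing on Appendix O, which gives thresholds for 255 pairs and 85 subjects. The Table 5 sentence on fulfilling all protocol requirements can equally mean this protocol's own requirements, 85 and 26–31.
- *Completed subjects would be discarded until 33 remain, with a loss of precision.* No passage instructs this, and it would breach quota 1. The listed exclusion reasons do not include reducing the sample to 33. The range adjustment and distribution exclusions turn on recruitment or observer pressures, not on device error. Any precision loss calculated for a cut to 33 would describe an assumed scenario, so none is given here.
- *Quota 3 misquotes Form 3.* Its reference to Form 3 may attach to the pressure bands, which Table 1 does show, and not to the counts. On that reading the citation is correct; on the other it is wrong. The wording allows both.

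**Conclusion.** The point holds as an internal contradiction in the sample-size and composition rules. Its direct effect is certain but limited: every sample that meets the 85-subject quotas violates eight mandatory conditions in Form 3, Table 1. The conclusion rests on two assumptions: that healthy adults over 25 count as a general adult population, which Form 3 supports, and that the form reproduced in the document is the one to be completed. The pass thresholds in Appendix O are defined and correctly scaled, so this does not invalidate the planned assessment. It should be corrected before analysis, so that nobody has to choose between the two rules with the results in hand.

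**What to change.** 1. In Form 3, Boxes 312 and 314–323, replace the total of 33 with the protocol's number (at least 85), and replace 10–12 with 26–31.
2. State in Form 3 and in the Data Analysis subsection that Appendix O supersedes all 33-subject and 99-measurement values in Form 3. This must cover Box 330 (sex totals and minimum), Table 3 (totals of 99 and the 22–44 limits) and Table 5. Editing Table 1 alone would leave the same values in those places.
3. In quota 3 of the Recruitment plan, cite Appendix O for the 26–31 counts and keep Form 3 only as the source of the pressure bands.

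When making Appendix O the governing table, the sponsor should confirm two limits that it carries over unscaled: the maximum difference of 19 between range counts (19 × 255/99 = 48.94) and the 4 permitted out-of-range pressures (4 × 85/33 = 10.30). The documents do not say whether keeping them was deliberate. The entry cut-off of 12 in Form 2 is a related leftover, and a statement confined to Form 3 would not reach it.

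The cost is wording only, with no added subjects, visits or procedures.
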